7 STUDY PROCEDURES

Subject Entry

Participants who meet the inclusion and exclusion will be asked to enroll in the study. The investigator or designee will explain the study purpose, procedures and responsibilities to the potential participant and provide sufficient opportunity to ask questions, while allowing adequate time for consideration of the information provided. Upon participant confirmation of interest, written informed consent will be obtained and the subject will be enrolled in the study. One copy of the informed consent document (ICD) will be retained with the subject's medical records and one copy will be provided to the subject.

Subject Cohort Selection:

Subjects with mild to moderate cataracts (Grade 1-2) who meet the inclusion criteria, will be assigned to Cohort 1. Subjects with severe cataracts (Grade 2+ - 3+) meeting the inclusion criteria will be assigned to cohort 2. Subjects with intermediate cataracts, which may qualify for either Cohort, will be assigned based on investigator discretion and clinical judgement since exact lens density judgment is impossible to determine prior to surgery.

Only 1 eye per subject will be enrolled into the study. Up to 100 subjects (100 eyes) will be enrolled into the first phase of the study and an additional 200 subjects (200 eyes) will be enrolled in the second phase of the study, for a total of 300 subjects (300 eyes). Subjects will

be enrolled in one of the two cohorts of this clinical investigation. For the first 100 eyes enrolled – up to 75 eyes in Cohort 1 and up to 75 eyes in Cohort 2. For the additional second phase of 200 eyes – up to 150 eyes per subject in Cohort 1 and up to 150 eyes in Cohort 2. Overall, for the 300 study eye investigation, there should be no more than 225 eyes in either Cohort 1 or 2.

Surgical Procedure

All subjects will undergo routine cataract surgical intervention with IOL implantation. All subjects will receive the standard of care preoperative and peri-operative medications and assessments. The procedure can be performed under either topical or peri/retrobulbar anesthesia per investigator discretion. Clear cornea cataract surgery will be performed with the following steps:

Study Eye

For each subject, one or both eyes may be treated; however, if both eyes are scheduled for treatment, then one eye will be designated as the “study eye” based on investigator discretion prior to any surgical intervention.

Study Visits

All subjects enrolled will return for defined follow-up visits pre- and post-operatively. Data collected from each scheduled and unscheduled (or interim) exam will be recorded on a Case Report Form (CRF).

Subjects who become ineligible for study participation after enrollment will be exited from the study and the reason for exit will be documented on the Subject Screening Log and noted as a screen failure.

Pre-Operative/Screening Visit

This visit can occur 0 to 60 days prior to surgery. The following information will be captured for the study eye at this visit:

- Demographic data (gender, age, race / ethnicity)
- Ocular history / ocular medications
- Cohort selection 1 or 2
- Identification of study eye (OS or OD)
- Cataract type and grade
- Manifest refraction and best-corrected visual acuity (BCVA)
- Slit lamp biomicroscopy
- Dilated pupil size measurement
- Goldmann tonometry
- Dilated fundus examination and C:D ratio assessment
- Central corneal pachymetry
- Macular OCT (optional)

Intraoperative

The following information will be captured for the study eye during surgery:

- Total lens removal time
- Total volume of irrigation fluid used
- Anesthesia type
- Other surgical procedures performed
- Device failure / malfunction
- Method / device used for cataract pre-segmentation
- MICOR-304 model used
- Type of viscoelastic used
- Total procedure time
- Any intraoperative AEs (capsule tear, corneal haze, other)

1 DAY Postoperative

This visit must occur at postoperative days 1-2. The following information will be captured for the study eye at this visit:

- Ocular medications

- UCVA (pinhole)
- Slit lamp biomicroscopy
- Goldmann tonometry
- Central corneal pachymetry
- AE assessment
- Macular OCT (optional)

1 WEEK Postoperative

This visit must occur at postoperative days 5-10. The following information will be captured for the study eye at this visit:

- Ocular medications
- Manifest BCVA
- Slit lamp biomicroscopy
- Goldmann tonometry
- Central corneal pachymetry
- AE assessment
- Macular OCT (optional)

1 MONTH Postoperative

This visit must occur at postoperative days 21-35. The following information will be captured for the study eye at this visit:

- Ocular medications
- Manifest BCVA
- Slit lamp biomicroscopy
- Goldmann tonometry
- Central corneal pachymetry
- Dilated fundus examination and C:D ratio assessment
- AE assessment
- Macular OCT (optional)

The examinations associated with each study visit are outlined and summarized in **Appendix 1** (Schedule of Events and Procedures) and a description of methodology for these examinations is provided in **Appendix 2** (Examination Procedures, Tests, Equipment and Techniques).

Unscheduled Visits

Unscheduled visits are those which are not required by the study protocol, but which occur due to a surgical procedure performed on the study eye, or a subject complaint regarding this eye. No specific testing is required at unscheduled visits; rather, the Investigator and/or qualified investigational staff will perform the procedures necessary to evaluate the subject at these visits. Clinical data from these visits will be recorded on the relevant CRF.

Subject Identification

The subjects will be identified by a five digit number comprised of a two-digit site number followed by a three-digit subject # (e.g., 01-001, 01-002, 01-003 etc.). The subject identification number will be assigned when informed consent is obtained.

Source Documents and Case Report Forms

Adequate original records will be maintained for the study. All original source documents will be retained at the site. The study sponsor, sponsor's representative, and appropriate regulatory authorities shall have access to the source documents as needed.

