2 STUDY SYNOPSIS

Study Objective

The purpose of this research study is to evaluate the clinical outcomes of the use of low-energy segment removal with a micro-interventional irrigation/aspiration port (MICOR-304) to evacuate the lens prior to intraocular lens insertion in subjects undergoing routine cataract surgery.

Study Population

Only 1 eye per subject will be enrolled into the study. Up to 100 subjects (100 eyes) will be enrolled into the first phase of the study and an additional 200 subjects (200 eyes) will be enrolled in the second phase of the study, for a total of 300 subjects (300 eyes). Subjects will be enrolled in one of the two cohorts of this clinical investigation. For the first 100 eyes enrolled – up to 75 eyes may be enrolled in Cohort 1 and up to 75 eyes in Cohort 2. For the additional second phase of 200 eyes – up 150 eyes may be enrolled in Cohort 1 and up to 150 eyes in Cohort 2. Overall, for the 300-study eye investigation, there should be no more than 225 eyes in either Cohort 1 or 2.

Study Design

This is multicenter, multi-cohort, prospective clinical study designed to provide longitudinal, observational, non-comparative clinical outcome data for mechanical non-phacoemulsification lens extraction using low-energy segment removal with a micro-interventional irrigation/aspiration port (MICOR-304) to evacuate the lens prior to intraocular lens insertion.

Subjects will be stratified into two Cohorts. Cohort 1 is comprised of eyes with mild-to-moderate cataracts only (Grade 1 to 2). Cohort 2 is comprised of eyes with moderate to more dense cataracts only (Grade 2+ to 3+).

Inclusion Criteria

1. Able to understand study requirements, willing to follow study instructions and willing to return for required study follow-up visits.
2. Willing and able to understand and complete the informed consent document
3. Subjects with a cataract grade of 1 to 3+ and are scheduled to undergo cataract surgery
4. Subjects \geq 18 years of age

5. Clear intraocular media, other than cataract

Exclusion Criteria for both Cohorts

1. Polar cataracts
2. Zonular instability
3. Subjects who have been diagnosed with dry eye which has been untreated and or would affect postoperative visual acuity outcomes (i.e., if the subject has had dry eye treatments / devices and has, or is undergoing treatment and deemed to be stable, they would be an eligible study candidate).

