6. STUDY POPULATION

Individuals will be assessed for study eligibility based on the criteria presented below:

Inclusion Criteria

1. Able to understand study requirements, willing to follow study instructions and willing to return for required study follow-up visits
2. Willing and able to understand and complete the informed consent document
3. Subjects with a cataract grade of 1 to 3+ and are scheduled to undergo cataract surgery
4. Subjects \geq 18 years of age
5. Clear intraocular media, other than cataract

Exclusion Criteria for both Cohorts

1. Polar cataracts
2. Zonular instability
3. Subjects who have been diagnosed with dry eye which has been untreated and or would affect postoperative visual acuity outcomes (i.e., if the subject has had dry eye treatments / devices and has, or is undergoing treatment and deemed to be stable, they would be an eligible study).
4. Concurrent participation or participation in any clinical trial up to 30 days prior to preoperative visit
5. Subjects that are pregnant, lactating or planning to become pregnant during the course of the study

Primary Endpoints

Efficacy: Total lens removal time and amount of irrigation solution fluid volume used during the surgical procedure.

- Total lens removal time is defined in two phases:
 - The beginning time starts when the surgeon enters the eye with the MICOR-304 to start the lens removal process and completing when the surgeon finishes the nucleus lens removal with the MICOR-304 before changing over to irrigation and aspiration.
 - The second phase of lens removal time is the irrigation and aspiration stage for cortex removal which starts when the irrigation and aspiration tip enters the eye and completion time is when the cortex is removed.
- Total irrigation solution volume will be recorded using the indicators on the waste bag which will have labels that have pre-defined markers to indicate milliliters (ml) of volume of irrigation solution used for the surgical procedure.

Safety: Rate of occurrence of intraoperative and postoperative adverse events (AE)

Secondary Endpoints

- UCVA on day 1,7,30
- Change in corneal thickness from baseline through Day 30
- Rate of occurrence of intraoperative and postoperative adverse events (AE)
- Results of slit lamp and fundus examinations, which are not considered to be AEs

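### Where both eyes are scheduled, the study eye is chosen at investigator discretion, which leaves the absolute time, volume and adverse event results open to a selection bias of unknown direction and size

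*Combined protocol and SAP*

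**What the plan says.** Section 7 (Study Eye) states "For each subject, one or both eyes may be treated". If both are scheduled, one of them is named the study eye "based on investigator discretion prior to any surgical intervention". The Synopsis limits the data to one eye: "Only 1 eye per subject will be enrolled into the study". No objective rule for choosing it (random, by laterality, or by order of surgery) appears in the documents.

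Other provisions that bear on the point:

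- The Synopsis describes the output as "longitudinal, observational, non-comparative clinical outcome data", so there is no control group.
- Section 6 gives the primary efficacy endpoints as "Total lens removal time and amount of irrigation solution fluid volume used during the surgical procedure". The primary safety endpoint is the adverse event rate.
- The Section 7 screening visit records, for the study eye, its identity, cataract type and grade, and dilated pupil size. The footnote to Appendix 1 confines all examinations to the study eye.
- Cohorts are defined by grade, and at full enrolment of 300 "there should be no more than 225 eyes in either Cohort 1 or 2". Eyes that could fit either cohort "will be assigned based on investigator discretion and clinical judgement since exact lens density judgment is impossible to determine prior to surgery".
- Section 8 plans descriptive statistics with 95% t intervals, and no test, margin or success criterion.

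**The concern.** In a single-arm study the reported mean time, mean volume and event rate are read as absolute values for the device. Whatever decides which eyes enter the data goes straight into those values, and no control arm cancels it.

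The requirement to designate before surgery removes one route to bias, choosing on the study eye's own outcome. It leaves another open. The study eye is named at the visit where grade, type and pupil size are assessed. An investigator planning surgery on both eyes would ordinarily know the same features of the fellow eye (an inference; the documents do not say so). The plan itself treats grade as a strong predictor: Section 8 expects a mean lens removal time of 5 minutes in Cohort 1 and 10 minutes in Cohort 2.

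If the choice leans one way, the estimates are off by a fixed amount. Going from 100 to 300 eyes narrows the intervals and leaves that amount unchanged, so coverage of the true mean worsens as the study grows.

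**Working it through.** **The plan's own figures.** Section 8 assumes SDs of 1 minute (Cohort 1), 2 minutes (Cohort 2) and 5 ml (volume), with 50 eyes per cohort. Width = 2 × t(0.975, 49) × SD/√50 gives 0.568 min, 1.137 min and 2.84 ml, against the stated 0.56, 1.14 and 2.8. For safety, 1 − 0.975^100 = 92.0%, consistent with the stated chance above 90%. These reproduce; the point is about design, not a wrong number.

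**Size of a possible shift.** Inputs:

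- SD 2 min for Cohort 2 lens removal time: Section 8.
- Between-eye correlation ρ = 0.5 to 0.7: assumption.
- Share of subjects with both eyes scheduled f = 0.30 to 0.60: assumption; the documents give no figure.
- Foresight r = 0.3 to 0.6, the correlation between the investigator's preoperative expectation for an eye and its actual time: assumption.
- The easier-looking eye is always chosen: assumption, made to obtain a bound in one direction.

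*Step 1, perfect foresight, bilateral subjects only.* The expected minimum of two correlated normal values lies SD × √((1 − ρ)/π) below the mean: 2 × √(0.5/π) = 0.798 min at ρ = 0.5 and 2 × √(0.3/π) = 0.618 min at ρ = 0.7.

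*Step 2, imperfect foresight, all subjects.* Multiply by f and by c, the correlation between the predicted and the actual difference between the two eyes. The value of c depends on how prediction errors relate across eyes.

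(a) If errors correlate between eyes as strongly as the times do, c = r:
- low end: 0.618 × 0.30 × 0.3 = 0.056 min
- high end: 0.798 × 0.60 × 0.6 = 0.287 min

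(b) If errors are independent between eyes, c = r√(1 − ρ)/√(1 − r²ρ):
- low end (ρ = 0.7, r = 0.3): c = 0.170; 0.618 × 0.30 × 0.170 = 0.03 min
- high end (ρ = 0.5, r = 0.6): c = 0.469; 0.798 × 0.60 × 0.469 = 0.22 min

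Over both cases the range is about 0.03 to 0.29 min.

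*Step 3, comparison with precision.* Half-width = t(0.975, n − 1) × 2/√n.

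| Eyes in Cohort 2 | 95% CI half-width (min) | Shift, case (a) | Shift, case (b) |
|---|---|---|---|
| 75 | 0.46 | 0.06 to 0.29 | 0.03 to 0.22 |
| 150 | 0.32 | 0.06 to 0.29 | 0.03 to 0.22 |
| 225 | 0.26 | 0.06 to 0.29 | 0.03 to 0.22 |

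The shift exceeds the half-width only in case (a), with every input near its upper limit and Cohort 2 near its cap. At that corner the bias is 0.287/(2/√225) = 2.15 standard errors, and coverage of the nominal 95% interval falls to roughly 43%. At the low end of either case coverage is barely affected.

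*Other endpoints.* Under the same assumptions the shift is 0.03/2 to 0.29/2, or about 0.015 to 0.145 SD. That is about 0.015 to 0.145 min in Cohort 1 (SD 1) and about 0.1 to 0.7 ml for volume (SD 5). For adverse events the documents give no basis for a size. Purely as an illustration, if chosen eyes had a 2.0% rather than a 2.5% event rate, the chance of at least one event in 100 eyes would be 1 − 0.98^100 = 86.7%; in 300 eyes it would be 1 − 0.98^300 = 99.8%.

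**The case against.** The strongest reply has five parts.

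1. *Grade is already controlled.* Cohorts are formed by grade, and with no more than 225 of 300 eyes in one cohort the other has at least 300 − 225 = 75. This stands as far as it goes. A reader might infer that the study could simply be filled with easy eyes; the cohort structure does not allow that. It does not stop the choice of the easier eye within a cohort, for example 2+ over 3+, and placing intermediate eyes is itself discretionary.

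2. *Foresight is limited.* Section 7 says exact density cannot be judged before surgery. This stands, and is why foresight is taken well below 1.

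3. *Direction is unknown.* A reader might infer that the results are biased in the device's favour. The documents show that selection is possible, not that it will occur or which way it would go. Naming the denser eye would lengthen the mean time. Nor do they say that the person who designates the eye is the one who operates.

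4. *The data can reveal selection.* Type, grade and pupil size are recorded for each study eye, so results can be described or standardised by them. This partly stands. Those records describe the eye chosen, not the one passed over; fellow-eye findings, bilateral status and the reason for the choice are not among the listed data.

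5. *Nothing turns on it.* There is no test or success criterion, and 0.29 min is 2.9% of the expected 10 minutes. This limits the seriousness. It does not remove the point, because the absolute estimates are the study's whole output.

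**Conclusion.** The point holds as an avoidable weakness in design. Section 7 leaves the study eye to discretion for subjects with both eyes scheduled, and neither the timing of the designation nor the cohort caps close that route. Lens removal time, fluid volume and the adverse event rate can be biased; neither direction nor amount can be settled from the documents.

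The range of 0.03 to 0.29 minutes for Cohort 2 rests on assumed values for the bilateral share, between-eye correlation and foresight, on the easier eye always being favoured, and on how prediction errors relate between eyes. It runs from negligible to about the size of the half-width at 225 eyes. A claim that the bias generally outweighs the sampling error is not supported: at 75 and 150 eyes the whole range lies below the half-width, and at 225 only one extreme corner exceeds it. The change is worth making because it is cheap and a larger sample does not help.

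**What to change.** In Section 7 (Study Eye), where both eyes are eligible and scheduled, replace investigator discretion with designation from a pre-generated random list, applied after consent and before any surgery. A fixed laterality rule set independently of the investigator, such as one keyed to the subject number given at consent, is an alternative; it is more foreseeable than a random list. The order of surgery stays a care decision. For that reason a rule naming the first eye scheduled would not be enough: whoever sets the order would still choose the study eye.

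Recording bilateral status and the fellow eye's grade is an optional addition that would let readers compare chosen with unchosen eyes.

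The cost is a sentence or two and a short list for each site, with no extra eyes. Investigators lose the choice of which eye is reported, and results may look slightly less favourable. If the designated eye is operated on second, the site must check that its surgery still falls within the 0 to 60 day screening window.

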8 STATISTICAL METHODS

Analysis Plan

Primary and secondary endpoints will be analyzed with descriptive statistics. Point estimates and confidence intervals will be calculated for each outcome. 95% confidence intervals for lens removal time and irrigation fluid volume will be calculated based on a t distribution.

Frequency tabulations of safety outcomes will be made at the 1 week and 1-month follow-up evaluations.

Sample Size

The sample size for this study is based on the following:

For safety, the pooled sample of 100 eyes will have a greater than 90% chance of detecting one or more rare adverse events, i.e., those with an expected rate of occurrence of 2.5%.

We anticipate that for Cohort 1 (grades 1 – 2) the mean lens removal time will be approximately 5 minutes, with standard deviation of 1 minute, and for Cohort 2 (grades 2+) the mean lens removal time will be about 10 minutes, with standard deviation 2 minutes. Under

these assumptions a sample of 50 eyes will produce a confidence interval width of approximately 0.56 minutes for Cohort 1 and 1.14 minutes for Cohort 2.

For Irrigation Fluid Volume we anticipate a mean of 30ml with a standard deviation of approximately 5ml for both Cohorts. Under these assumptions, a sample of 50 eyes will produce a confidence interval width of approximately 2.8ml for each Cohort.

Adverse Events

The number of subjects reporting at least 1 AE of a given type will be summarized. AEs not listed that occur during the study will be added to the summary of AEs. Summaries will also be provided for AEs considered to be related to the device. Each AE will be summarized by incidence and percentage.

Central Corneal Pachymetry

Central corneal pachymetry data will be summarized with N, mean, standard deviation, minima, median, and maxima. A 95% confidence interval will be provided for the change and percentage change from baseline. Change between two consecutive visits will also be summarized.

Slit Lamp and Fundus Exam Findings

Slit lamp, and fundus examination findings at scheduled follow-up visits will be tabulated such that the number and percentage of subjects in each category will be summarized.

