4. Concurrent participation or participation in any clinical trial up to 30 days prior to preoperative visit.
5. Subjects that are pregnant, lactating or planning to become pregnant during the course of the study

Primary Endpoint

Efficacy: Total lens removal time and amount of irrigation solution fluid volume used during the surgical procedure.

- Total lens removal time is defined in two phases:
 - The beginning time starts when the surgeon enters into the eye with the MICOR-304 to start the lens removal process and completing when the surgeon finishes the nucleus lens removal with the MICOR-304 before changing over to irrigation and aspiration.
 - The second phase of lens removal time is the irrigation and aspiration stage for cortex removal which starts when the irrigation and aspiration tip enters the eye and completion time is when the cortex is removed.
- Total irrigation solution volume will be recorded using the indicators on the waste bag which will have labels that have pre-defined markers to indicate milliliters (ml) of volume of irrigation solution used for the surgical procedure.

Safety: Rate of occurrence of intraoperative and postoperative adverse events (AEs)

Secondary Endpoints

- UCVA on day 1
- BCVA on days 7, 30
- Change in corneal thickness from baseline through Day 30
- Rate of occurrence of intraoperative and postoperative adverse events (AE)
- Results of slit lamp and fundus examinations, which are not considered to be AEs

- Total procedure time: defined as the beginning time when the surgeon makes the first incision in the eye and completion time is when the eye speculum is removed at the end of the procedure.

Schedule of Visits

Screening visit, intraoperative visit, post-operative day 1, day 7, day 30.

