4 STUDY OBJECTIVES

The purpose of this research study is to characterize the clinical outcomes of mechanical and ultrasound-assisted lens fragmentation techniques in routine cataract surgery. The study will provide longitudinal, observational, non-comparative clinical outcomes data for mechanical lens fragmentation techniques.

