5. STUDY DESIGN

This study protocol is a dual cohort, prospective, multi-center, interventional study whose goal is to evaluate the clinical and surgical outcomes of mechanical lens fragmentation techniques. The study is planned for up to 10 investigational sites. Only 1 eye per study subject will be enrolled into the study.

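### Do the plain 95% t intervals for lens removal time and irrigation volume need a correction for site?

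*Combined protocol and SAP*

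**What the plan says.** Section 8, Analysis Plan, calls for descriptive statistics on the primary and secondary endpoints, and for the two primary efficacy outcomes specifies that "95% confidence intervals for lens removal time and irrigation fluid volume will be calculated based on a t distribution". Section 8, Sample Size, applies this to planning. With an SD of 1 minute, "a sample of 50 eyes will produce a confidence interval width of approximately 0.56 minutes for Cohort 1"; the matching figures are 1.14 minutes for Cohort 2 (SD 2 minutes) and 2.8 ml for irrigation volume (SD 5 ml).

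Section 5 says "The study is planned for up to 10 investigational sites" and limits each subject to one eye. The Synopsis sets total enrolment at 300 eyes and adds that "there should be no more than 225 eyes in either Cohort 1 or 2". Section 7 builds the site number into every subject identifier.

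No visible section puts site into the analysis or names the population the intervals describe. Section 4 gives the aim as characterizing "clinical outcomes of mechanical and ultrasound-assisted lens fragmentation techniques in routine cataract surgery", and its next sentence describes the data as observational and non-comparative.

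**The concern.** Both outcomes depend on how a surgeon operates, so eyes from one site could be alike. The documents leave room for this in three places. Subjects with intermediate cataracts "will be assigned based on investigator discretion and clinical judgement" to a cohort. "Method / device used for cataract pre-segmentation" is recorded as something that can vary. The first timing phase ends by reference to the operator, "completing when the surgeon finishes the nucleus lens removal with the MICOR-304".

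If eyes within a site are positively correlated, the plain t interval leaves out the part of the uncertainty that comes from which sites took part. The mismatch grows with enrolment: precision was planned at 50 eyes per cohort, but 300 eyes with at most 225 in one cohort puts each cohort between 300 − 225 = 75 and 225 eyes, still from at most 10 sites. In a single-arm study with no hypothesis test, the estimate and its interval are the main efficacy result. A reader who takes the aim of studying routine cataract surgery as a claim about practice elsewhere would credit the study with too much precision.

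**Working it through.** **1. The plan's own figures.** Inputs from Section 8: n = 50, SD 1 and 2 minutes, SD 5 ml. Full width = 2 × t(0.975, n−1) × SD / √n, with t(0.975, 49) = 2.0096 and √50 = 7.0711.

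- Cohort 1 time: 2 × 2.0096 × 1 / 7.0711 = 0.568 min (plan: 0.56)
- Cohort 2 time: twice that, 1.137 min (plan: 1.14)
- Volume: five times that, 2.842 ml (plan: 2.8)

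The planning figures are right for independent eyes.

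**2. Two targets for the same interval.** Assume k equal sites, m = N/k eyes per site, total variance 1, and a between-site share equal to the ICC. Let DE = 1 + (m − 1) × ICC.

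- Variance of the mean about the wider-population mean: DE/N
- Variance of the mean about the participating-site mean: (1 − ICC)/N
- Expected sample variance used by the plain interval: (N − DE)/(N − 1)

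Take N = 50, k = 10, ICC = 0.10. Then DE = 1 + 4 × 0.10 = 1.40 and the expected sample variance is 48.6/49 = 0.992.

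- Wider target: 2.0096 × √(0.992/1.40) = 1.69 standard errors, about 91% coverage
- Participating sites: 2.0096 × √(0.992/0.90) = 2.11 standard errors, about 96.5% coverage

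For the participating sites the interval is slightly conservative, because the pooled SD already contains the between-site spread.

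**3. Simulation.** 20,000 studies per setting, normal outcomes, random site effect. Coverage of the plain 95% t interval for the wider target:

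| Eyes / sites in a cohort | ICC 0.02 | 0.05 | 0.10 | 0.20 |
|---|---|---|---|---|
| 50 / 10 | 94% | 93% | 90% | 85% |
| 50 / 5 | 93% | 90% | 84% | 76% |
| 75 / 10 | 94% | 91% | 87% | 80% |
| 150 / 10 | 92% | 87% | 80% | 68% |
| 225 / 10 | 90% | 82% | 73% | 60% |

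At ICC 0 it is 95% throughout. For the participating-site mean it is 95 to 97% in every one of these settings.

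**4. In clinical units.** Compare a t interval on site means (k − 1 df), half-width t(0.975, k−1) × SD × √(DE/N), with the plain one. Cohort 1, SD 1 minute, 10 sites, t(0.975, 9) = 2.262:

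- 50 eyes, ICC 0.10: 2.262 × √(1.40/50) = 0.378 against 0.284 min, a gap of 0.094 min, about 6 seconds
- 225 eyes, ICC 0.10: DE = 1 + 21.5 × 0.10 = 3.15; 2.262 × √(3.15/225) = 0.268 against 0.131 min, about 8 seconds
- 225 eyes, ICC 0.20: DE = 5.30; 2.262 × √(5.30/225) = 0.347 against 0.131 min, about 13 seconds

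With only 5 sites and 50 eyes at ICC 0.10, the full widths are 1.08 and 0.57 min, a half-width gap of about 15 seconds. Cohort 2 gaps are double, on an expected mean of 10 minutes. For volume at 50 eyes over 10 sites and ICC 0.10, the full widths are 3.79 and 2.84 ml, so the half-width grows by about 0.5 ml on an expected mean of 30 ml.

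**5. What a required site-clustered interval would cost.** A random-intercept model with Satterthwaite degrees of freedom gives a wider interval even when there is no clustering: 0.64 against 0.57 min on average with 10 sites of 5 eyes. At that size it estimates the site variance as zero in about 47, 37 and 25% of studies at ICC 0.02, 0.05 and 0.10, and then returns the plain interval. With unequal sites it also yields a second mean, weighted differently from the mean over eyes.

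**The case for a change.** The strongest case for a change is that a reported 95% interval ought to say what it covers, and that adding eyes at the same sites makes this one look better than it is for practice at large. At ICC 0.10, going from 50 to 150 eyes over 10 sites cuts the plain Cohort 1 width from 0.57 to 0.32 min (43%), but a mixed-model width only from 0.74 to 0.56 min (25%). Site is already in the subject identifier, so a clustered interval needs no new data.

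The arithmetic stands, and so does the observation that the target is unstated. What does not follow is that the planned interval is wrong. The wider target has to be supplied by the reader: routine cataract surgery names a procedure rather than a population of sites. A random-site model supports statements about other sites only if the participating sites can be treated as a sample of them, and no section says how sites are chosen. Whether to treat at most 10 sites as fixed or random in a descriptive study is a choice on which statisticians reasonably differ.

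The evidence for correlation is also thin. The timing points are tied to events in the operation, and recording the pre-segmentation method does not show that it differs by site. Section 7 introduces surgical steps that do not appear in the available text, and Appendix 2 on techniques is blacked out, so how far technique is standardised cannot be judged.

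**Conclusion.** No change to the plan is needed. The t intervals and planning widths are correct for independent eyes, and the intervals keep at least their nominal coverage, apart from simulation error, for the mean at the participating sites. They fall short only if read as describing other sites and if eyes within a site are positively correlated. The documents neither claim the first nor establish the second.

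Under that reading, with 10 equal sites, normal outcomes and an ICC from 0.02 to 0.20, coverage runs from about 94% (50 eyes, ICC 0.02) to about 60% (225 eyes, ICC 0.20). The low end pairs the largest assumed correlation with the enrolment ceiling for one cohort. In units of the outcome, the 10-site half-width gaps worked out above are about 6 to 13 seconds for Cohort 1 and double that for Cohort 2, and no decision in the study depends on them. Fewer sites would make the gap larger.

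What is missing is a statement of target, which a competent analyst supplies by describing the results as those of the participating sites; the site number in each identifier lets anyone tabulate eyes, mean and SD by site. A site-clustered interval is a defensible extra, but it trades a wider interval and a second mean for an inference the plan does not set out to make.
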